13.5.1. Definition of Adverse Events

Adverse Event Definition:

 • An AE is any untoward medical occurrence in a patient or clinical investigation subject, temporally associated with the use of a medicinal product, whether or not considered related to the medicinal product. • NOTE: An AE can therefore be any unfavorable and unintended sign (including an abnormal laboratory finding), symptom, or disease (new or exacerbated) temporally associated with the use of a medicinal product.

Events meeting AE definition include:

 • Any abnormal laboratory test results (hematology, clinical chemistry, or urinalysis) or other safety assessments (e.g., ECGs, radiological scans, vital signs measurements), including those that worsen from baseline, and felt to be clinically significant in the medical and scientific judgement of the investigator. • Exacerbation of a chronic or intermittent pre-existing condition including either an increase in frequency and/or intensity of the condition. • New conditions detected or diagnosed after study treatment administration even though it may have been present prior to the start of the study. • Signs, symptoms, or the clinical sequelae of a suspected interaction. • Signs, symptoms, or the clinical sequelae of a suspected overdose of either study treatment or a concomitant medication (overdose per se will not be reported as an AE/SAE unless this is an intentional overdose taken with possible suicidal/self-harming intent. This should be reported regardless of sequelae). • "Lack of efficacy" or "failure of expected pharmacological action" per se will not be reported as an AE or SAE. However, the signs and symptoms and/or clinical sequelae resulting from lack of efficacy will be reported if they fulfil the definition of an AE or SAE. • The signs and symptoms and/or clinical sequelae resulting from lack of efficacy will be reported if they fulfil the definition of an AE or SAE. Also, "lack of efficacy" or "failure of expected pharmacological action" also constitutes an AE or SAE.

Events NOT meeting definition of an AE include:

 • Any clinically significant abnormal laboratory findings or other abnormal safety assessments which are associated with the underlying disease, unless judged by the

Events NOT meeting definition of an AE include:

- investigator to be more severe than expected for the subject's condition.
- The disease/disorder being studied or expected progression, signs, or symptoms of the disease/disorder being studied, unless more severe than expected for the subject's condition.
 - Medical or surgical procedure (e.g., endoscopy, appendectomy): the condition that leads to the procedure is an AE.
 - Situations where an untoward medical occurrence did not occur (social and/or convenience admission to a hospital).
 - Anticipated day-to-day fluctuations of pre-existing disease(s) or condition(s) present or detected at the start of the study that do not worsen.

13.5.2. Definition of Serious Adverse Events

If an event is not an AE per definition above, then it cannot be an SAE even if serious conditions are met (e.g., hospitalization for signs/symptoms of the disease under study, death due to progression of disease, etc).

Serious Adverse Event (SAE) is defined as any untoward medical occurrence that, at any dose:

a. Results in death

b. Is life-threatening

NOTE:

The term 'life-threatening' in the definition of 'serious' refers to an event in which the subject was at risk of death at the time of the event. It does not refer to an event, which hypothetically might have caused death, if it were more severe.

c. Requires hospitalization or prolongation of existing hospitalization

NOTE:

- In general, hospitalization signifies that the subject has been detained (usually involving at least an overnight stay) at the hospital or emergency ward for observation and/or treatment that would not have been appropriate in the physician's office or out-patient setting. Complications that occur during hospitalization are AEs. If a complication prolongs hospitalization or fulfills any other serious criteria, the event is serious. When in doubt as to whether "hospitalization" occurred or was necessary, the AE should be considered serious.
- Hospitalization for elective treatment of a pre-existing condition that did not worsen from baseline is not considered an AE.

d. Results in disability/incapacity

Serious Adverse Event (SAE) is defined as any untoward medical occurrence that, at any dose:

NOTE:

- The term disability means a substantial disruption of a person's ability to conduct normal life functions.
- This definition is not intended to include experiences of relatively minor medical significance such as uncomplicated headache, nausea, vomiting, diarrhea, influenza, and accidental trauma (e.g. sprained ankle) which may interfere or prevent everyday life functions but do not constitute a substantial disruption

e. Is a congenital anomaly/birth defect

f. Other situations:

- Medical or scientific judgment should be exercised in deciding whether reporting is appropriate in other situations, such as important medical events that may not be immediately life-threatening or result in death or hospitalization but may jeopardize the subject or may require medical or surgical intervention to prevent one of the other outcomes listed in the above definition. These should also be considered serious.
- Examples of such events are invasive or malignant cancers, intensive treatment in an emergency room or at home for allergic bronchospasm, blood dyscrasias or convulsions that do not result in hospitalization, or development of drug dependency or drug abuse

g. Is associated with liver injury and impaired liver function defined as:

- ALT \geq 3xULN and total bilirubin^{*} \geq 2xULN (>35% direct), **or**
- ALT \geq 3xULN and INR^{**} $>$ 1.5.

* Serum bilirubin fractionation should be performed if testing is available; if unavailable, measure urinary bilirubin via dipstick. If fractionation is unavailable and ALT \geq 3xULN and total bilirubin \geq 2xULN, then the event is still to be reported as an SAE.

** INR testing not required per protocol and the threshold value does not apply to subjects receiving anticoagulants. If INR measurement is obtained, the value is to be recorded on the SAE form.

See [Appendix 3](#) for the required liver chemistry follow-up instructions

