5.6.1. Risk Assessment

For FF/VI the following risks and the mitigation strategy as applicable to asthma patients were taken from the summary of safety concerns in the European Union – Risk Management Plan (EU-RMP). For FF/VI the data/rationale for the risk were derived from the 2014 Investigator's Brochure, from an integrated analysis of key RELVAR studies (Integrated Summary of Safety for Fluticasone Furoate/Vilanterol v02 DBL 31 Jan 2014), from the RMP version 6.2 and in the RELVAR/BREO ELLIPTA Prescribing Information for countries in which FF/VI is approved for marketing.

Potential Risk of Clinical Significance	Summary of Data/Rationale for Risk	Mitigation Strategy
Investigational Product (IP) [FF/VI]		
Pneumonia in patients with asthma	
The incidence of pneumonia in patients with asthma was uncommon. The incidence (adjusted for exposure) seen with FF/VI 100/25 microgram strength (8.5/1000 patient years) was similar to placebo (9.3/1000 patient years). No risk factors were identified.
 
In an analysis performed on the 18 key studies in subjects with asthma pneumonia was reported by 0.5% (13 of 2369) of subjects who received FF/VI 100/25 subjects and 0.2% (2 of 1070) of subjects who received placebo.^a
	
The risk of pneumonia in asthma patients is very low and is consistent with the risk of other ICS. Subjects are not at an increased risk in this study, since they enter the study stable on an existing ICS treatment. Subjects are alerted to the potential risk of pneumonia in the informed consent. Investigators are informed of the risk in Section 1.2.3 (Asthma Clinical Studies) and Section 5.3.3 (Safety in Asthma Clinical Studies) of the IB. Subjects with concurrent respiratory disease are excluded from the study.

Asthma related intubations and deaths	
This is a class effect of LABA in asthma. This has not been observed for FF/VI.
 
An FDA meta-analysis of LABA vs. no LABA (60,954 patients in 110 trials) by age group on a composite endpoint of asthma-related deaths, intubations, and hospitalizations (asthma
	
Subjects with a history of life-threatening asthma are excluded from the study.

Potential Risk of Clinical Significance	Summary of Data/Rationale for Risk	Mitigation Strategy

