8.4.2. Asthma Exacerbations

Severe asthma exacerbations should not be recorded as an AE unless they meet the definition of an SAE (Section 13.5.2). For the purposes of this study, severe asthma exacerbations will be collected and recorded on the exacerbations log in the eCRF. The treatment details must also be recorded in the eCRF.

The time period for collection of severe asthma exacerbations will begin from the time of randomization (first receipt of investigational product) and will end after the 7-day follow-up period has been completed.

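### Protocol 8.4.2, 13.5.1 and 13.5.2 conflict on whether a serious asthma exacerbation is an SAE, so the same admission or death can fall inside or outside 24-hour reporting

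*Protocol*

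**What the plan says.** Three sections of the protocol bear on how a serious asthma event is classified.

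- **8.4.2 (Asthma Exacerbations):** "Severe asthma exacerbations should not be recorded as an AE unless they meet the definition of an SAE". Severe exacerbations go on a dedicated eCRF log instead. On timing: "The time period for collection of severe asthma exacerbations will begin from the time of randomization".
- **13.5.1 (Definition of Adverse Events):** a worsening of a chronic or intermittent condition, in frequency or intensity, is listed as an AE. The same section lists as not an AE: "The disease/disorder being studied or expected progression, signs, or symptoms of the disease/disorder being studied, unless more severe than expected" for that subject.
- **13.5.2 (SAE definition):** its opening rule reads "If an event is not an AE per definition above, then it cannot be an SAE even if serious conditions are met". The examples in brackets are "hospitalization for signs/symptoms of the disease under study, death due to progression of disease".

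Section 6.4.1 defines a severe exacerbation to include an asthma admission or emergency visit that needed systemic corticosteroids. Section 8.4.1.1 collects AEs and SAEs from the start of run-in and sets 24 hours for reporting SAEs. Section 8.4.1.4 requires the Death section of the eCRF for every death, SAE or not, within one week of its being reported. Section 5.6.1 lists asthma-related intubation and death among the risks of FF/VI: "This is a class effect of LABA in asthma", although it adds that this has not been seen with FF/VI.

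**The concern.** A site with an asthma admission to classify starts at 8.4.2, which sends it to 13.5.2. The first example it meets there of an event that cannot be an SAE is an admission for the disease under study. Section 13.5.1 supports either answer, and nothing in the protocol says what degree of asthma worsening is expected in this population.

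Two things are at stake. The first is prompt reporting: only SAEs carry the 24-hour rule, and the events in doubt are of the kind that 5.6.1 singles out for the LABA class. The second is the safety tables: SAP 8.1.1 (Table 5) and Appendix 13 keep SAE displays separate from severe-exacerbation displays, so an event that one site reports as an SAE and another does not would make the SAE counts depend on the site.

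**Working it through.** The protocol gives no figure for this point. The check is a cross-reading, followed by a small sum for the exposure involved.

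**1. Does the chain of rules close on itself?** Section 8.4.2 makes AE *recording* depend on SAE status. Section 13.5.2 makes SAE status depend on the AE *definition* in 13.5.1. That definition makes no reference to SAE status, so the chain ends at 13.5.1.

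**2. What does 13.5.1 decide for asthma?** It points both ways. The inclusion covers a flare of a chronic condition. The exclusion covers the studied disease and its expected signs, unless worse than expected. The bullets on lack of efficacy also disagree: one says it is not reported as such, the last says it does constitute an AE or SAE.

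**3. Where each event ends up under the two readings:**

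| Event | Read as an exacerbation, or worse than expected | Read as expected asthma |
|---|---|---|
| Admission with systemic corticosteroids, after randomisation | SAE, 24 hours, SAE tables; also on the log | Log only, no reporting clock |
| Same admission in run-in | SAE, 24 hours | Not an AE or SAE; log not yet open |
| Asthma death | SAE, 24 hours; also Death section | Death section, one week |
| Severe exacerbation meeting no seriousness criterion, after randomisation | Log | Log |
| Same event in run-in | Kept off the AE page by 8.4.2; log not yet open | Same |

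The last row does not depend on judgement. Under 8.4.2 as written, such a run-in event has neither an AE record nor a log entry. Section 6.2.2 makes it a bar to randomisation and 6.4.1 a reason for withdrawal, so the event itself may appear only as the reason for run-in failure or withdrawal.

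**4. How much follow-up precedes the log?** Inputs are from 10.2.1 (275 screened, 20% screen failure, 70% run-in failure) and 5.2 (4-week run-in, 2-week periods, 2-week washout, about 1 week of follow-up).

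- Entering run-in: 275 × (1 − 0.20) = 220. Randomised: 220 × (1 − 0.70) = 66. Both match the protocol.
- Run-in failures: 220 − 66 = 154.
- Run-in time: 220 × 4 = 880 subject-weeks.
- Time with the log open: 66 × (2 + 2 + 2 + 1) = 462 subject-weeks.
- Share before the log opens: 880 / (880 + 462) = 880 / 1,342 = 0.66.

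These are upper limits, because early exits are ignored in both parts. In total, 1,342 / 52 is about 26 subject-years, so the number of events will be small. The documents give no asthma admission rate, so no expected count is calculated.

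**The case against.** The strongest reply is that the text already leads to the right answer. Section 8.4.2 is the only asthma-specific rule and presupposes that some exacerbations are SAEs. The 13.5.2 examples sit under a condition, that the event has already failed 13.5.1, so they cannot displace that test. Entrants have FEV₁ of at least 70% predicted, no exacerbation needing oral corticosteroids in the 12 weeks before Visit 1 and no overnight asthma admission in the 6 months before it, so an admission is hard to call expected. Section 13.5.2 also gives emergency treatment of allergic bronchospasm as an example of a serious event. Severe exacerbations are tabulated by treatment (SAP Tables 3.24 to 3.26, Listing 28), and the LABA is given only after randomisation, when the log is open.

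Much of this stands. A reader might infer that the rules are circular, that an asthma admission has no route to SAE status, that the 13.5.2 examples override the worse-than-expected clause, or that every asthma admission is lost. The documents do not support any of these. The AE definition stands alone, and an event judged an exacerbation or worse than expected is an SAE from the start of run-in. Nor do run-in events vanish as a rule: SAEs and reasons for failure are required for run-in failures (6.3), and SAP Listing 16 covers AEs outside the ITT population.

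The reply does not remove the conflict. It needs the site to prefer one part of 13.5.1 to another and to read past an example that names the event in hand. The log and the Death section capture data, but neither carries the 24-hour rule.

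**Conclusion.** The concern holds as an inconsistency in the current text. A hospitalised or fatal asthma event can be placed inside or outside 24-hour SAE reporting, each with textual support, depending on whether the investigator treats it as an exacerbation or as expected disease. Separately, a run-in severe exacerbation not classed as an SAE has neither an AE record nor a log entry. That gap spans up to about two thirds of the planned subject-time, if the recruitment assumptions in 10.2.1 hold and 8.4.2 is read as applying before randomisation, since its AE-recording sentence has no time limit.

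The size is modest. Few events are expected, and after randomisation both deaths and severe exacerbations are still recorded. The run-in is on FP alone, so that gap concerns the completeness of safety reporting and not the LABA comparison. Classification is made under double-blind treatment in a crossover, so there is no evident reason for it to favour one arm. The effect would be incomplete, site-dependent SAE counts and late notification of individual cases. The change is worth making because it corrects a stated rule at almost no cost.

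**What to change.** Reconcile the three sections in a protocol amendment:

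- **13.5.2:** remove the disease-under-study examples, or state that they do not apply to asthma exacerbations.
- **8.4.2:** state that an exacerbation meeting any seriousness criterion is recorded and reported as an SAE from the start of run-in, as well as on the log.
- **8.4.2:** open the exacerbation log at the start of run-in.
- **13.5.1:** while the text is open, settle the conflicting bullets on lack of efficacy.

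In the SAP, Appendix 4 applies the AE treatment states, including pre-treatment, to exacerbations, so no new derivation is needed. Listing 28 is restricted to the ITT population and would need a counterpart for run-in failures, as Listing 16 provides for AEs.

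The cost is a few sentences, a note to sites, earlier use of an existing eCRF page, one extra listing and possibly one or two more SAE forms.

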13.5.3. Definition of Cardiovascular Events

Cardiovascular Events (CV) Definition:

Investigators will be required to fill out the specific CV event page of the CRF for the following AEs and SAEs:

- Myocardial infarction/unstable angina
- Congestive heart failure
- Arrhythmias
- Valvulopathy
- Pulmonary hypertension
- Cerebrovascular events/stroke and transient ischemic attack
- Peripheral arterial thromboembolism
- Deep venous thrombosis/pulmonary embolism
- Revascularization

13.5.4. Recording of AEs and SAEs

AEs and SAE Recording:

- When an AE/SAE occurs, it is the responsibility of the investigator to review all documentation (e.g., hospital progress notes, laboratory, and diagnostics reports) relative to the event.
- The investigator will then record all relevant information regarding an AE/SAE in the CRF
- It is **not** acceptable for the investigator to send photocopies of the subject's medical records to GSK in lieu of completion of the GSK, AE/SAE CRF page.
- There may be instances when copies of medical records for certain cases are requested by GSK. In this instance, all subject identifiers, with the exception of the subject number, will be blinded on the copies of the medical records prior to submission of to GSK.
- The investigator will attempt to establish a diagnosis of the event based on signs, symptoms, and/or other clinical information. In such cases, the diagnosis will be documented as the AE/SAE and not the individual signs/symptoms.
- Subject-completed Value Evidence and Outcomes questionnaires and the collection of AE data are independent components of the study.
- Responses to each question in the Value Evidence and Outcomes questionnaire will be treated in accordance with standard scoring and statistical procedures detailed by the scale's developer.

- The use of a single question from a multidimensional health survey to designate a cause-effect relationship to an AE is inappropriate.

13.5.5. Evaluating AEs and SAEs

Assessment of Intensity

The investigator will make an assessment of intensity for each AE and SAE reported during the study and will assign it to one of the following categories:

- Mild: An event that is easily tolerated by the subject, causing minimal discomfort and not interfering with everyday activities.
- Moderate: An event that is sufficiently discomforting to interfere with normal everyday activities
- Severe: An event that prevents normal everyday activities. - an AE that is assessed as severe will not be confused with an SAE. Severity is a category utilized for rating the intensity of an event; and both AEs and SAEs can be assessed as severe.
- An event is defined as 'serious' when it meets at least one of the pre-defined outcomes as described in the definition of an SAE.

Assessment of Causality

- The investigator is obligated to assess the relationship between study treatment and the occurrence of each AE/SAE.
- A "reasonable possibility" is meant to convey that there are facts/evidence or arguments to suggest a causal relationship, rather than a relationship cannot be ruled out.
- The investigator will use clinical judgment to determine the relationship.
- Alternative causes, such as natural history of the underlying diseases, concomitant therapy, other risk factors, and the temporal relationship of the event to the study treatment will be considered and investigated.
- The investigator will also consult the Investigator Brochure (IB) and/or Product Information, for marketed products, in the determination of his/her assessment.
- For each AE/SAE the investigator **must** document in the medical notes that he/she has reviewed the AE/SAE and has provided an assessment of causality.
- There may be situations when an SAE has occurred and the investigator has minimal information to include in the initial report to GSK. However, **it is very important that the investigator always make an assessment of causality for every event prior to the initial transmission of the SAE data to GSK.**
- The investigator may change his/her opinion of causality in light of follow-up information, amending the SAE data collection tool accordingly.

- The causality assessment is one of the criteria used when determining regulatory reporting requirements.

Follow-up of AEs and SAEs

- The investigator is obligated to perform or arrange for the conduct of supplemental measurements and/or evaluations as may be indicated or as requested by GSK to elucidate as fully as possible the nature and/or causality of the AE or SAE.
- The investigator is obligated to assist. This may include additional laboratory tests or investigations, histopathological examinations or consultation with other health care professionals.
- If a subject dies during participation in the study or during a recognized follow-up period, the investigator will provide GSK with a copy of any post-mortem findings, including histopathology.
- New or updated information will be recorded in the originally completed CRF.
- The investigator will submit any updated SAE data to GSK within the designated reporting time frames.

13.5.6. Reporting of SAEs to GSK

SAE reporting to GSK via electronic data collection tool

- Primary mechanism for reporting SAEs to GSK will be the electronic data collection tool
- If the electronic system is unavailable for greater than 24 hours, the site will use the paper SAE data collection tool and fax it to the Medical Monitor
- Site will enter the serious adverse event data into the electronic system as soon as it becomes available.
- The investigator will be required to confirm review of the SAE causality by ticking the 'reviewed' box at the bottom of the eCRF page within 72 hours of submission of the SAE.
- After the study is completed at a given site, the electronic data collection tool (e.g., InForm system) will be taken off-line to prevent the entry of new data or changes to existing data
- If a site receives a report of a new SAE from a study subject or receives updated data on a previously reported SAE after the electronic data collection tool has been taken off-line, the site can report this information on a paper SAE form or to the Medical Monitor by telephone.
- Contacts for SAE receipt can be found at the beginning of this protocol on the Sponsor/Medical Monitor Contact Information page.

SAE reporting to GSK via paper CRF

- Facsimile transmission of the SAE paper CRF is the preferred method to transmit this information to the Medical Monitor
- In rare circumstances and in the absence of facsimile equipment, notification by telephone is acceptable, with a copy of the SAE data collection tool sent by overnight mail
- Initial notification via the telephone does not replace the need for the investigator to complete and sign the SAE CRF pages within the designated reporting time frames.
- Contacts for SAE receipt can be found at this beginning of the protocol on the Sponsor/Medical Monitor Contact Information page.

13.6. Appendix 6: Modified List of Highly Effective Methods for Avoiding Pregnancy in Females of Reproductive Potential (FRP) and Collection of Pregnancy Information

This list does not apply to FRP with same sex partners, when this is their preferred and usual lifestyle or for subjects who are and will continue to be abstinent from penile-vaginal intercourse on a long term and persistent basis.

- Contraceptive subdermal implant
- Intrauterine device or intrauterine system
- Oral Contraceptive, either combined or progestogen alone [Hatcher, 2007]
- Injectable progestogen [Hatcher, 2007]
- Contraceptive vaginal ring [Hatcher, 2007]
- Percutaneous contraceptive patches [Hatcher, 2007]
- Male partner sterilization with documentation of azoospermia prior to the female subject's entry into the study, and this male is the sole partner for that subject [Hatcher, 2007].
- Male condom plus partner use of one of the contraceptive options below:
 - Contraceptive subdermal implant
 - Intrauterine device or intrauterine system
 - Oral Contraceptive, either combined or progestogen alone [Hatcher, 2007]
Injectable progestogen [Hatcher, 2007]
 - Contraceptive vaginal ring [Hatcher, 2007]
 - Percutaneous contraceptive patches [Hatcher, 2007]

This is an all inclusive list of those methods that meet the GSK definition of highly effective: having a failure rate of less than 1% per year when used consistently and, correctly and, when applicable, in accordance with the product label. For non-product methods (e.g. male sterility), the investigator determines what is consistent and correct use. The GSK definition is based on the definition provided by the ICH [ICH, M3 (R2) 2009].

The investigator is responsible for ensuring that subjects understand how to properly use these methods of contraception.

